6.3 Demographic data and medical history

Demographic data include age, sex, and self-reported race/ethnicity. Medical history comprises clinically significant diseases, surgical interventions, history of cancer (including prior antineoplastic treatments and procedures), history of smoking, alcoholism, drug addiction, as well

as any medications (e.g., prescribed drugs, over-the-counter drugs, medicinal plants, homeopathic remedies, or food supplements) used by the patient in the 28 days prior to screening visit.

6.4 Efficacy assessments

6.4.1 Tumor and response evaluations

All measurable and evaluable lesions should be assessed and documented at the screening visit and re-assessed at each subsequent tumor evaluation. Tumor assessments will be performed at screening, every 9 weeks (\pm 7 days) for the first 12 months following first dose of study treatment, and every 12 weeks (\pm 7 days) thereafter until disease progression, treatment discontinuation, withdrawal of consent, the start of new anticancer treatment, death, or study termination by the Sponsor, whichever occurs first. The same radiographic procedures and technique must be used throughout the study for each patient.

Radiologic imaging performed during the screening period should consist of 1) CT scan of the chest, abdomen, and pelvis (MRI of the abdomen and pelvis with a non-contrast CT scan of the chest in patients for whom CT scans with contrast are contraindicated), 2) bone scan if a subject has a known history of bone metastases or has new bone pain during screening, and 3) any other imaging studies as clinically indicated by the treating physician [brain imaging during the trial should be performed in subjects with known brain metastases (every nine weeks for first year, then every 12 weeks) and those with worsening and/or new neurological symptoms].

Tumor assessments performed after the screening period should consist of 1) CT scan of the chest, abdomen, and pelvis (MRI of the abdomen and pelvis with a non-contrast CT scan of the chest in patients for whom CT scans with contrast are contraindicated), 2) bone scan if a subject develops new or worsening symptoms or if the site believes they have attained a complete response, and 3) any other imaging studies felt to be clinically indicated by the treating physician. All known sites of disease documented at screening should be re-assessed at each subsequent tumor evaluation.

After disease progression by RECIST v.1.1, if the site Investigator determines the subject is clinically stable and will benefit from continued treatment, the subject will then be managed by irRECIST as described in **Section 6.4.4** of the protocol.

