| Safety and efficacy assessments: | 
Efficacy assessments:
 
Disease assessments [computerized tomography (CT) of the chest, abdomen, and pelvis or magnetic resonance imaging (MRI) of the abdomen and pelvis with a non-contrast CT scan of the chest in patients for whom CT scans with contrast are contraindicated] will be performed using RECIST v.1.1 every 9 weeks (\pm 7 days) from the first dose of study treatment up to one year (more frequently if clinically indicated). All subjects who remain on treatment for a year will subsequently have imaging performed every 12 weeks (\pm 7 days). Imaging should continue to be performed until radiologic evidence of disease progression, treatment discontinuation, the start of new anti-cancer treatment, withdrawal of consent, death, or the end of the study, whichever occurs first.
 
Bone scans will also be used to assess bone metastases. If a subject has a known history of bone metastases or has new bone pain during screening, a bone scan should be obtained prior to study entry. A bone scan at follow-up is required only if they develop new or worsening symptoms or if the site believes they have attained a complete response. If a subject has no known metastatic disease in the bone or active symptoms, a bone scan at baseline is not needed.
 
Brain imaging during the trial should be performed in subjects with known brain metastases (every nine weeks for first year, then every 12 weeks) and those with worsening and/or new neurological symptoms.
 
After disease progression by RECIST v.1.1, if the site Investigator determines the subject is clinically stable and will benefit from continued treatment, the subject will then be managed by irRECIST.
 
Each assessment will be performed as scheduled according to the calendar regardless of any dosing delay to prevent the introduction of bias into the assessment of efficacy. Failure to perform any of the
 |

| | |
|-----------|--|
| | 
required disease assessments will result in the inability to determine disease status for that time point.
 
Safety assessments:
 
The occurrence and maximum grade of adverse events (AEs) observed throughout the study will be listed. . Any AEs that the Investigator reports as unrelated to the drug will also be reported. In this study, AEs will be assessed according to the NCI CTCAE v.4.0.3.
 |

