3 STUDY DESIGN

3.1 Description of study design

This is a multicenter, open-label, phase II clinical trial to evaluate the efficacy and safety of the combination of MK3475 (pembrolizumab) and eribulin in HR-positive/HER2-negative MBC patients previously treated with anthracyclines and taxanes.

The study population consists of female patients age \geq 18 years with advanced HR-positive/HER2-negative breast cancer who have received at least one, but not more than two, prior chemotherapeutic regimens for treatment of locally recurrent and/or metastatic disease. Prior therapy must have included an anthracycline and a taxane in any combination or order and either in the early or metastatic disease setting unless contraindicated for a given patient. Previous anti-hormonal therapy in the metastatic disease setting is mandatory.

In the absence of disease progression or unacceptable toxicity, treatment with MK3475 (pembrolizumab) and eribulin will continue based on physician criteria. MK3475 (pembrolizumab) and eribulin may be discontinued for toxicity independently of each other in the absence of disease progression.

A participant must be discontinued from study treatment but continue to be monitored in the study for any of the following reasons:

- Completion of 35 treatments (approximately 2 years) with pembrolizumab. Please see the specific conditions at section 5.3.5.

Note: The number of treatments is calculated starting with the first dose. Participants who stop the combination or pembrolizumab after receiving 35 doses may be eligible for retreatment if they progress after stopping study treatment provided they meet the requirements detailed in section 5.3.5. Participants may be retreated in the Second Course Phase (Retreatment) for up to an additional 17 cycles (approximately 1 year).

After 35 dose administrations, patients can continue on treatment with eribulin alone.

Tumor assessments per RECIST v.1.1 (see **Appendix 2**) and irRECIST (see **Appendix 3**) will be performed approximately every nine weeks (\pm 7 days) for the first 12 months and every 12

weeks (\pm 7 days) thereafter until disease progression, treatment discontinuation, the start of new anti-cancer treatment, withdrawal of consent, death, or the end of the study, whichever occurs first. Tumor assessments will be performed on the specified schedule regardless of treatment delays.

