- Tumor burden remains $\geq 20\%$ and at least 5 mm absolute increase compared to nadir.
- Non-target disease resulting in initial disease progression is worse (qualitative assessment).
- New lesion resulting in initial disease progression is worse (qualitative assessment).
- Additional new lesion(s) since last evaluation.
- Additional new non-target progression since last evaluation.

If repeat imaging confirms disease progression due to any of the scenarios listed above, subjects will be discontinued from study therapy. If repeat imaging does not confirm disease progression by irRECIST and the subject continues to be clinically stable, treatment may continue and follow the regular imaging schedule.

*Note: If a subject with confirmed radiographic progression per irRECIST, but the subject is achieving a clinically meaningful benefit, and there is no further increase in the tumor burden at the confirmatory tumor imaging, an exception to continue treatment may be considered following consultation with the Sponsor. In this case, if treatment is continued, tumor imaging should continue to be performed following the intervals as outlined in **Appendix 1**.*

*Note: In subjects who discontinue study treatment without documented disease progression, every effort should be made to continue monitoring their disease status by tumor imaging following the intervals as outlined in **Appendix 1** until the start of new anti-cancer treatment, disease progression, death, or the end of the study, whichever occurs first.*

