4. In subjects who discontinue study treatment without documented disease progression, every effort should be made to continue monitoring their disease status by tumor imaging following the intervals as outlined in footnote 3 until the start of new anti-cancer treatment, disease progression, death, or the end of the study, whichever occurs first. However, tumor evaluation will be done by the Investigator criteria and local practice according to the technical sheet of pembrolizumab during the suspension of the First Course Phase and during the Second Course Phase.
5. Blood test will be performed as per local standard of care and clinical indication before treatment administration. These values should be included: hemoglobin, hematocrit, red blood cell count, platelet count, and WBC count with differential count (ANC, lymphocytes, monocytes, eosinophils, and basophils), coagulation, chemistry with renal function analysis (serum creatinine), liver function (AST, ALT, ALP, GGT, total and direct bilirubin), glucose, sodium, potassium, calcium, chloride, magnesium, uric acid, total protein, albumin, and lactate dehydrogenase.
6. Not repeat in Cycle 1, Day 1 if done in day -3 to day 1.
7. Urinalysis include: Specific gravity, pH, glucose, protein, ketones, and blood
8. Every 2 cycles: Cycle 3 day 1, cycle 5 day 1, cycle 7 day 1, etc, before study treatment administration.
9. Serum pregnancy test within 14 days before Cycle 1, Day 1. Urine pregnancy test every two cycles thereafter.
10. Samples for translational study will be obtained at each time point; at screening, every three cycles of treatment (Cycle 4 day 1, cycle 7 day 1, Cycle 10 day 1, etc), and at the end of the study treatment only in the first course.

12. Day 8 visits can be omitted, at the Investigator's discretion, in those patients that permanently discontinue eribulin treatment and continue with pembrolizumab as single agent.

13. End of treatment visit (EOT) will be performed within 30 days after last study dose. Participants who are eligible for retreatment/crossover with pembrolizumab (as described in Section 5.3.5) may have up to two EOT visits, one after the Initial Treatment Period and one after the Second Course Treatment.

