Appendix I

Table 1. Censoring rules for PFS

Situation	Date of progression or censoring	Outcome
Progression documented between scheduled visits	Earliest of: 
• Date of radiological assessment showing new lesion (if progression is based on new lesion); or• Date of last radiological assessment of measured lesions (if progression is based on increase in sum of measured lesions); Or	Progressed
Death before first progression disease assessment	Date of death	Progressed
Death between adequate assessment visits	Date of death	Progressed
No progression	Date of last radiological assessment of measured lesions	Censored
Treatment discontinuation for undocumented progression	Date of last radiological assessment of measured lesions	Censored
Treatment discontinuation for toxicity or other reason*	Date of last radiological assessment of measured lesions	Censored
Death or progression after more than one missed visit *	Date of last radiological assessment of measured lesions	Censored

* In accordance with these criteria death after the end of treatment visit will be considered as censored with the date of last radiological assessment of measured lesions.

Table 2. Censoring rules for PFS as assessed by investigator.

Situation	Date of progression or censoring	Outcome
No baseline assessment	Randomization + 1 day	Censored
Progression documented* between scheduled visits	Next scheduled visit	Progressed
No progression	Date of last visit with adequate assessment	Censored
Investigator's claim of progression*	Scheduled visit (or next scheduled visit if between visits)	Progressed
Treatment discontinuation for toxicity or other reason **	Date of last visit with adequate assessment	Censored
New anticancer treatment started with no claim of progression	Date of last visit with adequate assessment	Censored
Death before first progression disease assessment	Date of death	Progressed
Death between adequate assessment visits	Date of death	Progressed
Death after an extended lost-to-followup time (two or more missed assessments)**	Last visit with adequate assessment	Censored

* In addition to the progressions confirmed by radiological criteria, also the progressions evaluated by the investigator, without a radiological image confirming them, will be considered as PFS events.

** In accordance with these criteria death after the end of treatment visit will be considered as censored with the date of last adequate assessment.

Table 3. Censoring rules for OS

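### The protocol both stops and continues tumor imaging at treatment discontinuation, so a patient with stable disease only who stops before the week-27 scan may or may not count for CBR; separately, the SAP censors PFS at discontinuation

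*Protocol*

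**What the plan says.** Three places end imaging when treatment stops:

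- Synopsis, efficacy assessments: "Imaging should continue to be performed until radiologic evidence of disease progression, treatment discontinuation", followed by the other stopping events, whichever comes first.
- Protocol 3.1: assessments run "until disease progression, treatment discontinuation, the start of new anti-cancer treatment, withdrawal of consent, death, or the end of the study".
- Protocol 6.4.1: every 9 weeks for 12 months, then every 12 weeks "thereafter until disease progression, treatment discontinuation, withdrawal of consent, the start of new anticancer treatment, death, or study termination by the Sponsor".

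Two places say the opposite for patients who stop without progression:

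- The closing note of 6.4.4: "In subjects who discontinue study treatment without documented disease progression, every effort should be made to continue monitoring their disease status by tumor imaging", until new anticancer treatment, progression, death or end of study.
- Appendix 1, footnote 4: "every effort should be made to continue monitoring their disease status by tumor imaging following the intervals as outlined in footnote 3", with the same end points. The footnote then leaves tumor evaluation to local practice while the first course is suspended and during the second course.

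Nothing says which rule prevails. Protocol 5.3 adds that patients with both drugs withheld for more than 21 days are off study.

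The primary endpoint (protocol 8.2.1, SAP 6.1.1) counts CR, PR, or SD lasting at least 24 weeks, over all patients in the analysis set. Protocol 8.4 treats a missing binary outcome as non-response.

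For PFS, Tables 1 and 2 of SAP Appendix I each have a censoring row headed "Treatment discontinuation for toxicity or other reason", and their footnotes also censor deaths after the end-of-treatment visit. Protocol 6.4.3 defines PFS to progression or death from any cause, without such exceptions. For DoR, SAP 6.2.1 censors patients without progression or death and has no discontinuation rule.

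**The concern.** The imaging rule decides whether 24-week SD can be documented in a patient who stops treatment early, for example for toxicity. A site that follows 6.4.1 takes no further scans. A site that follows 6.4.4 does. Two patients with the same course of disease can therefore receive different values of the primary endpoint, and one patient can decide the trial: 18 of 44 fails and 19 of 44 passes.

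The same scans feed PFS and DoR. Protocol 8.4 relies on Kaplan-Meier methods provided that drop-out is unrelated to prognosis. That condition is doubtful for patients who stop for toxicity, and more so for deaths that are set aside.

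**Working it through.** **1. When 24-week SD can first be shown.** Scans fall at weeks 9, 18 and 27, each ±1 week. The second is at week 19 at the latest, which is before week 24. The third is at weeks 26 to 28. An on-schedule scan therefore first documents 24-week SD at weeks 26 to 28.

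**2. Who is affected.** Under the synopsis, 3.1 and 6.4.1, it is a patient whose only benefit is SD and who stops without progression before that third scan. A patient with CR or PR by then already counts under 8.2.1. One who stops after the third scan can qualify.

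**3. The plan's own design.** Inputs from protocol 8.1: null CBR 0.30, target 0.50, at least 17 of 39, 10% drop-out.

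- Type I error: P(X ≥ 17 | 39, 0.30) = 0.04998.
- Power: P(X ≥ 17 | 39, 0.50) = 0.8316.
- Inflation: 39 / (1 − 0.10) = 43.3, rounded up to 44.

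The design reproduces. Exact power is above the stated 80% because the binomial is discrete. With all 44 in the denominator, 18 gives p = 0.081 and 19 gives p = 0.044. The smallest passing count is 19, with power 0.8544.

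**4. Expected loss if imaging stops.** Let *d* be the share of patients who stop without progression before the third scan, and *s* the share of clinical benefit that is SD only. The documents give neither, so both are assumptions. If stopping is independent of benefit:

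- loss in CBR = 0.5 × s × d
- patients lost = 44 × 0.5 × s × d
- observed CBR = 0.5 × (1 − s × d)

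The low value of *d*, 3.4%, is borrowed from protocol 1.4.2 (discontinuation for neuropathy on eribulin). The high value, 10%, is illustrative.

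| d | s | Loss in CBR (points) | Patients of 44 | Power, 17/39 | Power, 19/44 |
|---|---|---|---|---|---|
| 0 | – | 0 | 0 | 83.2% | 85.4% |
| 3.4% | 0.5 | 0.85 | 0.4 | 80.3% | 82.7% |
| 3.4% | 1 | 1.7 | 0.7 | 77.3% | 79.7% |
| 10% | 0.5 | 2.5 | 1.1 | 74.1% | 76.5% |
| 10% | 1 | 5.0 | 2.2 | 63.0% | 65.1% |

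**5. Direction.** Lost cases can only lower the observed CBR. Power falls, and the chance of a false positive does not rise.

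**6. PFS and DoR.** The PFS censoring at discontinuation and at late deaths is written into SAP Appendix I, so it applies under either imaging rule. DoR has no such rule. There, censoring at discontinuation would follow from the absence of later scans.

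**The case against.** The 6.4.4 note and footnote 4 are the specific rules for patients who stop without progression, and protocol 3.3 describes a post-treatment phase that includes efficacy follow-up. One can fairly read the stop lists as loose drafting and conclude that imaging was meant to continue. That supports the direction of the fix. It does not remove the conflict, because a site reading the efficacy section alone may properly stop scanning.

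A reader might infer that patients who stop for toxicity cannot reach 24-week SD. That is true only under one of the two rules, and only for the patients in step 2.

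A reader might also multiply 44 by 3.4% to 10%, obtain 1.5 to 4.4 patients, and call it up to 10 points of CBR. That is a ceiling, reached only if every early stopper would otherwise have had SD-only benefit. The 3.4% is also an imperfect input: it is eribulin alone, one toxicity and any time. The protocol also lets one drug stop while the other continues (3.1, 6.2), and such a patient has not clearly discontinued study treatment.

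Finally, a reader might infer that the imaging conflict causes informative censoring of PFS, or that later scans would be discarded. The censoring stands regardless of the conflict. Table 1 censors at the last radiological assessment without saying whether that means the last before stopping. That the censoring is informative is a reasonable worry, but the documents give no data to size it.

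SAP 6.9 defines CBR without the 24-week condition, under which an earlier SD would count. That is a further inconsistency and does not resolve this one.

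**Conclusion.** The contradiction is in the current text and reaches the primary endpoint, because endpoint status can depend on which section a site follows. The expected effect is modest: about 1 to 5 points of CBR, or 0.4 to 2.2 of 44 patients, with power of the 17/39 rule between 80.3% and 63.0% instead of 83.2%. These figures rest on assumed values of *d* and *s*, on stopping being independent of benefit, and on all sites following the stop rule. The bias is conservative.

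The PFS censoring in SAP Appendix I is a separate departure from the protocol's definition, and correcting the imaging text alone would not remove it. Both should be corrected.

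**What to change.** **Protocol.** Delete treatment discontinuation from the imaging stop lists in the synopsis, 3.1 and 6.4.1, so that they match 6.4.4 and Appendix 1. Reconcile two further passages with this: the off-study wording in 5.3, by stating whether imaging follow-up continues for those patients, and the local-practice sentence in footnote 4. State what discontinuation means for imaging when only one drug stops. None of this changes a treatment rule.

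**SAP.** In Appendix I Tables 1 and 2, remove the row that censors at discontinuation for toxicity or other reason, and the footnotes on deaths after the end-of-treatment visit. Patients with no later event then fall under the existing no-progression row. State that, until new anticancer therapy, scans after stopping treatment count for CBR, and scans and deaths after stopping count for PFS and DoR. Table 2 already has a row for new anticancer treatment; Table 1 shows none and needs one. The current censoring can stay as a sensitivity analysis.

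**Cost.** Wording in both documents, plus scans for a few off-treatment patients that 6.4.4 and Appendix 1 already request.

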6.4.2 Objective response assessment

CBR is defined as the proportion of the subjects in the analysis set who have a complete response, partial response, and stable disease using RECIST v.1.1 for at least 24 weeks.

ORR is defined as the proportion of the subjects in the analysis set who have a complete response or partial response based on RECIST v.1.1:

- Complete response: Complete disappearance of all targets lesions. Any pathological lymph nodes (target or non-target) must have reduction in short axis to < 10 mm.
- Partial response: At least a 30% decrease in the sum of diameters of target lesions, taking as reference the baseline sum diameters.
- Stable disease: Neither sufficient shrinkage to qualify for partial response, nor sufficient increase to qualify for disease progression, taking as reference the smallest sum diameters while on study.
- Disease progression: At least a 20% increase in the sum of diameters of target lesions, taking as reference the smallest sum diameters while on study. The development of new, previously undetected lesions, is also considered progression.

DoR is defined as the time from documentation of tumor response until disease progression or death from any cause.

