2 STUDY OBJECTIVES AND ENDPOINTS

2.1 Primary objective

To assess the efficacy -as determined by the CBR (total number of objective responses plus stable disease for at least 24 weeks) based on RECIST v.1.1- of MK3475 (pembrolizumab) in combination with eribulin in patients with HR-positive/HER2-negative MBC who have previously received an anthracycline and a taxane (for either early or advanced disease), unless contraindicated, and between one to two lines of chemotherapy in the metastatic setting.

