8 STATISTICAL CONSIDERATIONS AND STATISTICAL ANALYSIS PLAN

8.1 Determination of sample size

A sample size of 44 evaluable patients will be accrued, with an exact single-stage phase II design. The primary endpoint for this study is the CBR. CBR will be evaluated according to the RECIST criteria v.1.1. The CBR of MK3475 (pembrolizumab) in combination with eribulin will be assessed with the exact binomial test. In designing the trial, a CBR of 30% is deemed to be unacceptable in this patient population [16]. In contrast, a CBR of 50% would be considered to be successful. At least 17 patients with clinical benefit among 39 patients will be adequate to justify the investigation of this strategy in further clinical trials. Considering a drop-out rate of 10%, a sample size of 44 patients will be needed to attain 80% power at nominal level of one-sided alpha of 0.05.

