8.2 Statistical plan

8.2.1 Primary efficacy endpoint

The primary endpoint is to evaluate the CBR. The CBR is defined as the number of patients with complete response, partial response, or stable disease for at least 24 weeks divided by the number of patients in the analysis set. Tumor response will be assessed every nine weeks for the first 12 months following first dose of study treatment, and every 12 weeks thereafter. Tumor response will be defined as best response, based on local Investigator's assessment according to the RECIST criteria v.1.1.

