6.1.1 Summary statistics

CBR is defined as the number of subjects with complete response (CR), partial response (PR) or stable disease (SD) for at least 24 weeks divided by the number of patients in the analysis set.

$$\text{CBR} = (\text{CR} + \text{PR} + \text{SD}) / \text{Total number of patients}$$

The CBR results will be presented as number and proportion of patients with clinical benefit and 95% CI of the proportion.

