- Frequencies for toxicities related to clinically significant laboratory values will be presented (for 2-5 CTCAE grades).

6.8 ***Statistical model assumptions***

The proportional hazards assumption in the Cox model will be checked.

6.9 ***Transformation of expected variables***

- The CBR is defined as the proportion of subjects who have best overall response of CR, PR or SD (by RECIST v.1.1):

$$\text{CBR} = (\text{CR} + \text{PR} + \text{SD}) / \text{Total of subjects}$$

- The ORR is defined as the proportion of subjects who have best overall response of CR or PR (by RECIST v.1.1):

$$\text{ORR} = (\text{CR} + \text{PR}) / \text{Total of subjects}$$

- The time to progression is defined as the difference between start of study drug (C1D1) and the progression date or death (whichever occurs first) or the last tumor assessment documented.

- The time to death is defined as the difference between start of study drug and the date of death.
- Duration of response (DoR) is defined as the difference between first documented CR or PR and the disease progression date (by RECIST v.1.1) or death.
- Duration of treatment is defined as the difference between the first dose administrated of study drug (eribulin and/or pembrolizumab) and the date of EOT visit. If no date of EOT is available, the last administration of study drug will be used.

6.10 *Handling of missing data*

There is no planned procedure of imputation of missing values in other variables. The analysis will be performed with the available data.

6.11 *Description of the softwares to be used for data analysis*

Statistical programming and analyses will be performed using the R statistical software version 3.1.3.

6.12 *Interim analysis protocol*

No interim analysis is planned.

6.13 *List of tables and figures*

The tables below are an approximated list of the tables and figures that will be shown in the statistical analysis. They will be able to modify as required.

List of tables:

Descriptive statistics for the age at the informed consent signature

Absolute and relative (%) frequencies for the race

Absolute and relative (%) frequencies for significant disease and surgical intervention (registered in medical history).

Absolute and relative (%) frequencies for toxic habits

Descriptive statistics for number of relapses

Absolute and relative (%) frequencies for hormonal receptors (ER, PR) and HER2 status

Descriptive statistics for Ki67

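### Protocol 6.4.2 reads most naturally as requiring complete and partial responses to last 24 weeks, the primary objective does not, and no passage says which CBR definition governs

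*Protocol*

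**What the plan says.** The documents word the primary endpoint in several ways.

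- **Primary objective** (Protocol synopsis and 2.1; SAP synopsis and 4.1): "total number of objective responses plus stable disease for at least 24 weeks". The duration belongs to SD, and every objective response counts.
- **Protocol 6.4.2**, the section on response definitions: subjects "who have a complete response, partial response, and stable disease using RECIST v.1.1 for at least 24 weeks". The duration follows the whole list.
- **Protocol 8.2.1**, the primary endpoint in the statistical section: "number of patients with complete response, partial response, or stable disease for at least 24 weeks", over the analysis set. It adds: "Tumor response will be defined as best response, based on local Investigator's assessment".
- **SAP 6.1.1**: "complete response (CR), partial response (PR) or stable disease (SD) for at least 24 weeks divided by the number of patients in the analysis set", followed by a formula that adds CR, PR and SD with no time condition. SAP 6.2.1 repeats the wording for PD-L1-positive patients and adds that response means best response.
- **SAP 6.9**: "The CBR is defined as the proportion of subjects who have best overall response of CR, PR or SD". There is no 24-week condition, even for SD, and the same bare formula follows.

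The decision rule is at least 17 patients with clinical benefit among 39 (Protocol 8.1 and 8.2.7; SAP 4.5 and 6.1.2).

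**The concern.** In 6.4.2 the reference to RECIST must apply to all three response categories. The duration phrase comes directly after it, so it most naturally applies to all three as well. On that reading a response that ends before 24 weeks is not clinical benefit; under the objective it is.

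The difference can arise under the trial's own schedule. Scans are nine weeks apart in the first year, so a PR at week 9 followed by progression at week 18 is counted in opposite ways.

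This is the primary endpoint of an open-label, single-arm trial with investigator-assessed response, judged against a fixed count. If the wording is left open, the choice could be made once the results are known. The point concerns the duration of CR and PR; how the duration of SD is measured is a separate question.

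**Working it through.** **1. The plan's own figures reproduce.** With X binomial on 39 patients:

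- P(X ≥ 17) at a CBR of 30% = 0.04998, which meets the one-sided 0.05.
- P(X ≥ 17) at a CBR of 50% = 0.832, above the 80% target because the exact test moves in steps.
- 39 / (1 − 0.10) = 43.3, rounded up to 44.

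One patient matters at the line: 17 of 39 gives p = 0.050 and 16 of 39 gives p = 0.094.

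**2. Inputs from the documents.**

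- Median duration of response (DoR), eribulin alone: 3.9, 4.1 and 5.6 months (Protocol 1.3.2), or about 17, 18 and 24 weeks.
- ORR 12%: eribulin arm of the phase III trial against physician's choice (Protocol 1.3.3). Pembrolizumab alone in ER-positive, PD-L1-positive disease also gave 12% (1.9).
- ORR 33.3%: the same combination in triple-negative disease (1.11).
- Scans every nine weeks in year one (6.4.1).

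**3. Assumptions that are not in the documents.** Response durations are exponential; first response is documented at week 9; true CBR is 50% under the objective's definition.

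**4. Formulas.**

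- Share of responders lost: f = 1 − 2^(−t / median DoR), with t in months.
- Patients affected = 44 × ORR × f.
- CBR under the stricter reading = 0.50 − ORR × f.
- Chance of success = P(X ≥ 17) on 39 at that CBR.

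**5. Base case.** Weeks 9 to 24 are 15 weeks, so t = 3.45 months. Then f = 0.458, 0.442 and 0.348 for medians of 3.9, 4.1 and 5.6 months.

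- ORR 12%: 44 × 0.12 = 5.3 responders, of whom 1.8 to 2.4 are affected. CBR is 45.8% to 44.5%, and the chance of success 67% to 61%.
- ORR 33.3%: 44 × 0.333 = 14.7 responders, of whom 5.1 to 6.7 are affected. CBR is about 38% to 35%, and the chance of success 29% to 17% at those rounded rates (31% to 16% unrounded).

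**6. How far the timing assumptions move this.**

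| Case | t (months) | f | Patients of 44, ORR 12% | Patients of 44, ORR 33.3% |
|---|---|---|---|---|
| Progression by week 24, response at week 9 | 3.45 | 0.35–0.46 | 1.8–2.4 | 5.1–6.7 |
| Only progression by the week-18 scan | 2.07 | 0.23–0.31 | 1.2–1.6 | 3.3–4.5 |
| First response at week 18 | 1.38 | 0.16–0.22 | 0.8–1.1 | 2.3–3.2 |
| The response itself must last 24 weeks | 5.52 | 0.50–0.63 | 2.6–3.3 | 7.3–9.2 |

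The last row is listed because 6.4.2 does not say whether the 24 weeks run from first dose or from first response.

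**The case against.** The strongest reply is that the rest of the text nearly settles the matter. The sentence in 6.4.2 is loose: taken literally, its "and" would require all three states in one patient, so close grammatical reading is unreliable, and the duration can be attached to SD alone. The objective is clear wherever it appears. Protocol 8.2.1 defines the primary endpoint and ties response to best response, which ordinarily carries no 24-week condition for CR or PR. Protocol 8.2.2 refers back to 6.4.2 and 6.4.3 only for PFS, OS, ORR and DoR. All of this stands, and it makes 6.4.2 the outlier. It does not remove the conflict, because no passage gives precedence and SAP 6.9 offers a third definition.

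The sizes are also open to challenge, and the challenge stands. The 33% ORR comes from another tumor subtype and has no DoR attached. The DoR figures are for eribulin alone, whereas the median was not reached with pembrolizumab in ER-positive disease (Protocol 1.9). Progression between weeks 18 and 24 would ordinarily be documented only at the week-27 scan.

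A reader might go further in two ways that the documents do not support:

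- **That the 30% and 50% design rates fit only one of the definitions.** The plan says "a CBR of 30% is deemed to be unacceptable in this patient population" and cites the phase III trial against capecitabine, but Protocol 1.3.3 gives only an objective response rate for that trial, with no CBR and no CBR definition. This cannot be checked.
- **That the result will turn on one or two patients.** One patient changes the p-value at the boundary, but nothing in the documents says the observed count will fall there.

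**Conclusion.** The conflict is real but narrower than a flat contradiction. Protocol 6.4.2, on its most natural reading, departs from the primary objective; 8.2.1 and SAP 6.1.1 lean to the objective; SAP 6.9 omits the duration; and nothing states which governs.

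About 2 to 7 of 44 patients could change status in the base case, and about 1 to 5 if only progression by the week-18 scan counts or responses start later. If CBR is 50% under the objective, the stricter reading cuts the chance of a positive result from 83% to about 61–67% at ORR 12%, or about 17–29% at ORR 33%. The second range is the unfavorable end of the base case, not an expectation. All these figures rest on borrowed ORR and DoR values, exponential durations and an assumed time of first response; the documents give no rate of short-lived response for this combination in this population.

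The sample size and decision rule are unaffected. This should be fixed before analysis as a matter of harmonization; it does not invalidate the design.

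**What to change.** Before analysis, put one sentence in Protocol 6.4.2 and 8.2.1 and in SAP 6.1.1, 6.2.1 and 6.9, following the stated objective:

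*CBR is the proportion of patients in the analysis set with a best response of CR or PR (of any duration), or with SD lasting at least 24 weeks, by RECIST v.1.1.*

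Change the CBR formulas in SAP 6.1.1 and 6.9 to match, so that the SD term counts only patients whose SD lasted at least 24 weeks. Leaving SAP 6.9 as it stands would keep two conflicting primary-endpoint definitions in the SAP.

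Report alongside the primary result how many of the counted responders progressed before week 24, so that a reader can see what the stricter reading would have given.

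The cost is one sentence repeated in five places, two edited formulas and one extra line in the results. It needs no new data and no change to the sample size.
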